5.5.4 CLINICAL HEPATITIS

Subjects should be followed until resolution of the AE.

5.5.4.1 Non-viral Hepatitis

Subjects should be monitored for the development of signs and symptoms of hepatitis, which include fatigue, malaise, anorexia, nausea, dark urine and clay-colored stools, bilirubinuria, jaundice and liver tenderness, with or without initially abnormal serum transaminase levels.

Subjects with these signs and symptoms should seek medical attention immediately and have liver function tests performed.

5.5.4.2 Viral Hepatitis

If acute viral hepatitis is diagnosed while on trial, the subject should be permanently withdrawn from the trial.

5.5.5 RENAL COMPLICATIONS

Investigators should closely monitor trial subjects for disturbances in serum creatinine, urine electrolytes and for abnormalities in urinalysis (e.g., proteinuria). If renal complications develop, subjects must be treated as clinically appropriate. The trial medication may be continued if the renal complication is considered not related to the treatment (including DRV/rtv and OBR) in the opinion of the investigator.

Renal impairment, including cases of acute renal failure and Fanconi syndrome, has been reported in association with the use of Viread® (tenofovir). The majority of these cases occurred in subjects with underlying systemic or renal disease, or in subjects taking nephrotoxic agents, however, some cases occurred in subjects without identified risk factors (please refer to the package insert of tenofovir for details).

5.5.6 NAUSEA (WITH OR WITHOUT VOMITING)

Although common, nausea after the initiation of ARV therapy usually subsides or resolves during the first few weeks of treatment.

Grade 1 nausea (transient [< 24 hours] or intermittent nausea with no or minimal interference with oral intake):

Subjects may continue with the trial medication and may be treated as needed with anti-emetics given orally or by suppository. If vomiting occurs in pediatric subjects, they should wait 15 to 30 minutes and then start hydration in frequently small amounts. Once vomiting has stopped for at least a few hours, solid food can be reintroduced.

Grade 2 nausea (persistent nausea resulting in decreased oral intake for 24-48 hours):

Subjects may continue with the trial medication and may be treated as needed with anti-emetics given orally or by suppository. If vomiting occurs in pediatric subjects, they should wait 15 to 30 minutes and then start hydration in frequently small amounts. Oral rehydration solution should not be used for more than 24 hours, other liquids with salt and sugars should be given. Once vomiting has stopped for at least a few hours, solid food can be reintroduced.

Grade 3 nausea (persistent nausea resulting in minimal oral intake for > 48 hours or aggressive rehydration indicated [e.g., intravenous fluids]):

Subjects developing grade 3 nausea will have all treatment (including DRV/rtv and background regimen) interrupted. The subject will be treated as needed with anti-emetics given orally or by suppository. All medication may be resumed when the nausea resolves to grade ≤ 2 .

Grade 4 nausea (life-threatening consequences [e.g., hypotensive shock]):

Subjects developing grade 4 nausea will discontinue treatment (including DRV/rtv and background regimen) and will be withdrawn from the trial.

5.5.7 DIARRHEA

Grade 1 diarrhea (transient or intermittent episodes of unformed stools or increase of ≤ 3 stools over baseline per 24-hour period):

Subjects may continue the trial medication. Loperamide and diphenoxylate can be administered. Pediatric subjects should start with the BRAT (bananas, rice, applesauce and toast) diet.

Grade 2 diarrhea (persistent episodes of unformed to watery stools or increase of 4-6 stools over baseline per 24-hour period):

Subjects may continue the trial medication. Loperamide and diphenoxylate can be administered. Pediatric subjects should start with the BRAT diet and increase the amount of fluids.

Grade 3 diarrhea (bloody diarrhea, increase of ≥ 7 stools per 24-hour period, or intravenous fluid replacement indicated):

Subjects with grade 3 diarrhea will have all treatment (including DRV/rtv and background regimen) interrupted. All medication (including DRV/rtv and background regimen) may be resumed when the diarrhea resolves to grade ≤ 2 .

Grade 4 diarrhea (life-threatening consequences [e.g., hypotensive shock]):

Subjects will permanently discontinue treatment (including DRV/rtv and background regimen) and will be withdrawn from the trial.

Note: Rare cases of acute renal insufficiency have been reported in patients receiving DRV/rtv and tenofovir as part of a combination HIV therapy, more specifically in cases where moderate to severe diarrhea resulted in dehydration. Special attention should be given to the appropriate clinical management of diarrhea, dehydration and electrolyte losses, if applicable. In certain cases, temporary interruption of HIV therapy may be appropriate until the condition has improved.

5.5.8 OTHER TOXICITIES

Grade 1

Subjects who develop a grade 1 AE or toxicity may continue intake of the trial medication.

Grade 2

Subjects who develop a grade 2 AE or toxicity may continue intake of the trial medication based on the investigator's clinical judgment.

Note: For grade 3 or 4 laboratory toxicities, subjects should have a confirmatory measurement within 48 hours after the laboratory results become available. This management scheme is for confirmed laboratory abnormalities and not for isolated events.

Grade 3

Subjects who develop a grade 3 AE or toxicity should interrupt all medications (including DRV/rtv and OBR) and may resume all therapy when the AE or laboratory abnormality resolved to within one grade level (\leq grade 2) of the subject's baseline. The following exceptions apply:

- subjects who experience an asymptomatic glucose elevation of grade 3 (See Section 5.6.1);
- subjects who experience asymptomatic triglyceride or cholesterol elevations of grade 3 (See Section 5.6.2);
- subjects who experience asymptomatic pancreatic amylase elevations of grade 3 with no past or active history of pancreatitis (provided lipase is within normal limits) (See Section 5.6.5);
- subjects who experience an AE that is considered not related or doubtfully related to the study medication.

Grade 4

Subjects experiencing a grade 4 AE or toxicity will permanently discontinue medication (including DRV/rtv and OBR).

The following exceptions apply:

- subjects who experience asymptomatic triglycerides elevations of grade 4 (see also Section 5.2.5);
- subjects who experience an AE that is considered not related or doubtfully related to the trial medication.

5.6 Toxicity Management for Specific Adverse Events with Concomitant Antiretroviral Agents

Participating investigators are strongly encouraged to follow the guidelines and to apply the same safety measures for subjects participating in this trial.

Toxicity management is at the discretion of the investigator, and is to take into account the protocol-defined procedures defined under 5.6.1, 5.6.2, 5.6.3, 5.6.4, 5.6.5, and 5.6.6, and the local standard clinical practice.

After termination of data collection, toxicity management will be performed per local standard of care and documented in the subject's medical records only.

The information below does not imply that the respective adverse events are only related to the concomitant ARV therapy, since a contribution of DRV cannot be excluded.

5.6.1 Hyperglycemia

```
Grade 3: 13.89-27.75 mmol/L (251-500 mg/dL);
Grade 4: > 27.75 mmol/L (> 500 mg/dL).
```

Management decisions should be based on fasted results. Subjects with persistent grade 3 or 4 glucose elevations despite appropriate anti-hyperglycemic treatment should be permanently discontinued with the exception of subjects with pre-existing diabetes. Appropriate clinical management of hyperglycemia must be started in a timely fashion, if applicable.

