5.2.5 REMOVAL OF SUBJECTS FROM THERAPY OR ASSESSMENT

A subject **may** be withdrawn from the trial if:

- 1. An SAE occurs.
- 2. The subject fails to comply with the protocol requirements or to cooperate with the investigator.
- 3. The subject starts disallowed treatment (see Section 5.3.12). The sponsor should be contacted to evaluate the need for withdrawal.
- 4. The subject demonstrates lack or loss of treatment response during the trial.

A subject **must** be withdrawn from the trial if:

- 1. The parent(s) or legal representative(s) withdraw(s) consent, or the subject withdraws consent or assent.
- 2. The investigator considers it, for safety reasons, in the best interest of the subject that he or she be withdrawn.
- 3. Pregnancy has been determined.
- 4. The subject is diagnosed with acute hepatitis A, B, or C infection after baseline. For details on monitoring and management of hepatitis, see Section 5.5.4.

- 5. The subject experiences a grade 3 or 4 cutaneous reaction/rash (according to the DAIDS scale; see Section 7.2, Addendum 2: DAIDS Grading Table). For details on monitoring and management of cutaneous reaction/rash, see Section 5.5.1.
- 6. The subject experiences a grade 4 AE considered at least possibly related to DRV/rtv or a confirmed grade 4 laboratory abnormality (according to the Division of AIDS [DAIDS] scale; see Section 7.2, Addendum 2: DAIDS Grading Table) considered at least possibly related to DRV/rtv. Exceptions are, unless clinical assessment foresees an immediate health risk to the subject:
- 7. Subjects with asymptomatic triglyceride grade 4 elevations (see Section 5.6.2). The subject experiences a persistent grade 3 or 4 glucose elevation despite appropriate anti-hyperglycemic treatment (except if the subject has pre-existing diabetes; see Section 5.6.1)
- 8. The subject experiences a confirmed grade 4 pancreatic amylase elevation or a confirmed grade 3 or grade 4 lipase elevation, which persists after 14 days after the interruption of the trial medication, or if the toxicity recurs more than twice (see also Section 5.6.5.2). The subject experiences, after trial medication interruption because of a confirmed grade 3 increase in alanine aminotransferase (ALT) or aspartate aminotransferase (AST), a confirmed recurrence of grade 3 or 4 increase in ALT or AST. For subjects with hepatitis B or C coinfection present at baseline, refer to Section 5.5.3 for toxicity management plans.

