5.7 Statistical Methods Planned and Determination of the Sample Size

5.7.1 SAMPLE SIZE CALCULATION

Since the objective of the trial is only to provide continued access to DRV/rtv for HIV-1 infected adult or pediatric subjects who previously received DRV/rtv in a clinical (parent) trial, who continue to benefit from using it, and who live in a country where DRV is not commercially available for the subject, is not reimbursed, or is not accessible through another source (e.g., access program, government program), and since the trial is not set up to show a specific statistical hypothesis, a sample size calculation is not applicable.

Data from this trial may be included in safety updates.

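### The protocol does not say how its withdrawal rules interact for a related, confirmed grade 4 glucose elevation: criterion 6 of 5.2.5 (and, less firmly, 5.5.8) sets one condition, criterion 7 and 5.6.1 another.

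*Protocol*

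**What the plan says.** Four places in the protocol bear on a grade 4 glucose value.

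- **5.2.5, mandatory withdrawal, criterion 6:** "The subject experiences a grade 4 AE considered at least possibly related to DRV/rtv or a confirmed grade 4 laboratory abnormality", with the laboratory abnormality also required to be at least possibly related. The exception that completes this criterion is "Subjects with asymptomatic triglyceride grade 4 elevations (see Section 5.6.2"). It is printed at the start of item 7.
- **5.2.5, mandatory withdrawal, criterion 7:** withdrawal for a "persistent grade 3 or 4 glucose elevation despite appropriate anti-hyperglycemic treatment (except if the subject has pre-existing diabetes"), with a pointer to 5.6.1.
- **5.5.8 Other Toxicities:** "Subjects experiencing a grade 4 AE or toxicity will permanently discontinue medication (including DRV/rtv and OBR"). There are two exceptions at grade 4: "subjects who experience asymptomatic triglycerides elevations of grade 4 (see also Section 5.2.5"), and adverse events judged unrelated or doubtfully related. Glucose appears among the exceptions only at asymptomatic grade 3, with a pointer to 5.6.1.
- **5.6.1 Hyperglycemia:** "Subjects with persistent grade 3 or 4 glucose elevations despite appropriate anti-hyperglycemic treatment should be permanently discontinued", again excepting pre-existing diabetes. Grade 4 is defined as > 27.75 mmol/L (> 500 mg/dL).

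On the analysis side, Protocol 5.7.2.3 and SAP 3.2 and 4.1.1 summarize discontinuations, their reasons, and adverse events leading to discontinuation.

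**The concern.** Criteria 6 and 7 are both mandatory and both reach grade 4 glucose, but they ask different questions. Criterion 6 asks whether the value is confirmed and related. Criterion 7 asks whether the elevation has persisted despite treatment and whether the subject was already diabetic. An investigator whose diabetic subject has a related grade 4 value, or whose subject's value falls once treated, finds a mandatory withdrawal in one item and a narrower condition or an exemption in the next. Nothing says which prevails.

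What is at stake is mainly the subject. The trial exists to continue a treatment from which subjects benefit where they cannot otherwise obtain it, so both an unintended withdrawal and an unintended continuation matter. The statistical consequence is secondary: whether such an event enters the discontinuation counts could depend on how the site read the protocol.

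**Working it through.** The protocol plans no hypothesis test ("the trial is not set up to show a specific statistical hypothesis, a sample size calculation is not applicable"), so there is no figure to reproduce. The check sets the rules side by side for one fixed event: a glucose value that is confirmed, grade 4, and at least possibly related to DRV/rtv.

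**Step 1: rule out a grading difference.** The fasting and nonfasting glucose rows of the DAIDS table (Protocol 7.2) and 5.6.1 give the same grade 4 threshold, > 500 mg/dL. The rules therefore describe the same event.

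**Step 2: cross the two conditions that criterion 7 and 5.6.1 add.**

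| Persistent despite treatment | Pre-existing diabetes | Criterion 6 and 5.5.8 | Criterion 7 and 5.6.1 |
|---|---|---|---|
| yes | no | stop | stop |
| yes | yes | stop | exempt |
| no | no | stop | condition not met |
| no | yes | stop | condition not met |

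**Step 3: count.** Criterion 6 and 5.5.8 call for stopping in 4 of 4 cases. Criterion 7 and 5.6.1 call for it in 1 of 4. The difference is 4 − 1 = 3 cases. These are cells of a table, not frequencies; the documents do not say how often any of them occurs.

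**Step 4: apply the two possible readings.**

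- *Cumulative:* each criterion is sufficient alone. Criterion 6 decides all four cases, and the treat-first condition and diabetes exemption are inert for related grade 4 events, although criterion 7 and 5.6.1 both name grade 4.
- *Specific over general:* criterion 7 and 5.6.1 govern glucose. Criterion 6 is then overridden in three of the four cases, although its exception names triglycerides and leaves glucose out.

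**Step 5: look for text that chooses between them.** None was found. Section 5.5.8 defers to 5.6.1 for glucose at asymptomatic grade 3 and is silent at grade 4. The Amendment GEN-I rationale, used here only as evidence of intent, cuts both ways. It describes the glucose rule as turning on persistence and repeats the diabetes exception, but it also presents the rule as an extension of the withdrawal criteria.

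**Step 6: limit the scope.** If the event is unrelated or doubtfully related, criterion 6 does not apply and 5.5.8 exempts it. The difficulty is confined to related events.

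**The case against.** The strongest reply is that the passages do not contradict each other. The items in 5.2.5 are alternatives, each sufficient alone. Neither criterion 7 nor 5.6.1 says that withdrawal follows in no other circumstance, and neither says that treatment may go on. Where the protocol does mean to permit continuation it says so, as 5.6.2 does for asymptomatic lipid elevations. On this view criterion 7 simply adds persistent grade 3 elevations and events not attributed to DRV/rtv. The diabetes exemption still has work to do, since an event better explained by concomitant disease is classed as doubtful under Part II, 1.2 and so falls outside criterion 6.

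Much of this stands. A reader might infer that one passage orders withdrawal while another permits the same subject to stay on treatment. The documents do not support that: it turns silence into permission. But the cumulative reading is nowhere stated, and it empties two express conditions for related grade 4 events.

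A second reply is that 5.5.8 covers other toxicities, while hyperglycemia has its own section. Sections 5.5 and 5.6 are also introduced as subject to investigator discretion, and 5.6.1 uses advisory wording. That weakens the 5.5.8 leg, although 5.5.8 itself treats glucose as within its reach by excepting it at grade 3. It does not touch criteria 6 and 7, which are both mandatory.

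A third reply is that Amendment 2 makes the point moot, because toxicity management moves to local standard of care once data collection ends. That provision sits in 5.5 and 5.6. The sentence in 5.2.5 that names Amendment 2 concerns how termination is documented; it does not suspend the withdrawal list while DRV is still supplied.

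Finally, items 6 and 7 are visibly run together, which may be an artefact of numbering or text extraction. The glucose sentence nevertheless reads as a criterion in its own right, and the argument does not depend on the layout.

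**Conclusion.** The point holds as an unresolved interaction between rules, not as a proven direct contradiction. For a confirmed, related grade 4 glucose elevation, the mandatory list in 5.2.5 contains two differently conditioned criteria, and the toxicity sections repeat the split. Two reasonable readings differ in three of the four combinations of persistence and diabetes, so investigators following the protocol could handle the same subject differently.

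A reader might go further and infer that handling did differ between sites, or that the discontinuation summaries are materially distorted. The documents support neither. They give no frequency for such events. Adverse events leading to discontinuation are one of four descriptive safety summaries in Protocol 5.7.2.3, and there is no hypothesis to bias. Under Amendment 2 the next planned visit is the last with CRF data, and Protocol 5.7.2 allows no statistical analysis after that. The SAP already describes conduct in the past tense. A wording change now would alter few analysed discontinuations, if any. Laboratory safety results were not transferred to the database (SAP 1.2), so laboratory values cannot be used to sort events by rule.

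The conclusion assumes that the exception printed at the start of item 7 belongs to criterion 6, and that 5.2.5 stays in force while DRV is supplied. It merits a clarification request because it bears on subject safety and is cheap to settle. It is not among the most serious faults.

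**What to change.** Reconcile 5.2.5 criteria 6 and 7, 5.5.8 and 5.6.1 so that one consistent rule applies to a related, confirmed grade 4 glucose elevation. State in 5.2.5 how criteria 6 and 7 interact for glucose, repeat any exception in each of the places where the rule appears, and cross-refer between them. Separating the text now run together in items 6 and 7 would help. Which clinical rule applies is for the sponsor to decide; this review takes no position.

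The cost is clarification wording in the protocol. No change to data collection, the SAP or the planned outputs is needed.

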5.6.2 HYPERTRIGLYCERIDEMIA, HYPERCHOLESTEROLEMIA AND LDL CHOLESTEROL INCREASE

```
Hypertriglyceridemia grade 3: 8.49-13.56 mmol/L (751-1200 mg/dL); grade 4: > 13.56 mmol/L (> 1200 mg/dL).

Hypercholesterolemia grade 3: > 7.77 mmol/L (> 300 mg/dL); grade 4: not applicable.
```

LDL cholesterol increase grade 3: ≥ 4.91 mmol/L (≥ 190 mg/dL); grade 4: not applicable.

Management decisions should be based on fasted results. Subjects who experience grade 3 or 4 asymptomatic triglyceride or cholesterol elevations may continue to receive the trial medication unless clinical assessment foresees an immediate health risk to the subject.

Hypertriglyceridemia, hypercholesterolemia and LDL cholesterol increase should be treated according to the specific guidelines for treating HIV-positive subjects (see Section 7.5Addendum 5: Lipid Abnormalities)¹³. Current treatment guidelines (eg, The National Cholesterol Education Program [NCEP] guidelines) specify different lipid thresholds for intervention for different degrees of cardiovascular risk. The presence or absence of other significant cardiovascular risk factors, which include smoking, age, family history of premature cardiovascular disease, diabetes, hypertension, low high density lipoprotein (HDL) cholesterol, and prior history of cardiovascular disease should be taken into account. Appropriate clinical management of hyperlipidemia in the setting of HIV disease should be started in a timely fashion, if applicable.

For the OBR, the respective package inserts should be consulted for contraindicated medications or medications that are not recommended for concomitant use.

For an overview of allowed and disallowed medication, please refer to Section 5.3.5, and the respective sections in the IB of DRV.

5.6.3 LACTIC ACIDOSIS

The relevance of asymptomatic lactic acid elevations is unclear, and lactates are not part of the routine safety evaluations for this trial. Routine lactate monitoring is not currently recommended. However, lactate monitoring should be performed if there is a clinical suspicion of lactic acidosis (see description below).

A sometimes-fatal syndrome of lactic acidosis, often associated with evidence of hepatic steatosis, is a recognized but rare complication of NRTI therapy. This syndrome is felt to be secondary to mitochondrial toxicity induced by the inhibitory effect of NRTIs on DNA polymerase gamma, a key enzyme needed for mitochondrial DNA synthesis. Current knowledge regarding this syndrome is incomplete. Obesity and prolonged NRTI exposure may be risk factors. Females are also at increased risk. Symptoms of lactic acidosis are frequently non-specific (e.g., fatigue, weakness, hyperventilation and fever), but in the majority of cases also involve symptoms suggestive of hepatic dysfunction such as nausea, vomiting, abdominal or epigastric discomfort, abdominal distension, hepatomegaly, and new-onset elevated liver enzymes. A high index of suspicion may be required to diagnose this condition. Alternatively, it is possible that unwarranted concern may be raised by over-interpretation of lactic acid levels. NRTI toxicity is only one cause of lactic acidosis. Type "B" lactic acid elevations or those without clinically apparent tissue hypoxia are also seen in the context of diabetes, uremia, liver disease, infections, malignancies, alkaloses, and drug and toxin ingestion of substances such as ethanol, methanol, ethylene glycol, and salicylates.

The following case definition of lactic acidosis will be used in this protocol:

Symptomatic Hyperlactatemia

New, otherwise unexplained, and persistent (≥ 2 weeks) occurrence of 1 or more of the following symptoms:

- Nausea and vomiting
- Abdominal pain or gastric discomfort
- Abdominal distention
- Increased liver function tests
- Unexplained fatigue
- Dyspnea

and

- Lactate level $> 2 \times ULN$, confirmed by repeat lactate level analysis

Note: All lactates > 2 × ULN should be repeated as soon as possible, generally within 1 week. Lactate levels should not be assessed following physical exertion as this causes elevated lactate levels and may confound assessment of the clinical significance of these findings. If the second result confirms hyperlactatemia (> 2 × ULN) in subjects with symptoms as described above, the subjects should immediately discontinue their medication (DRV/rtv

and background regimen). Standard management should be initiated with follow-up to resolution. If causality is related to the background regimen only and **not** to DRV/rtv, the NRTIs must be changed (see Section 5.3.5) and subjects should continue DRV/rtv if treatment is re-initiated. If causality is (also) related to DRV/rtv, subjects must be withdrawn

Processing of the lactate needs to be done according to strict guidelines both in the preparation of the patient (ideally, fasting and with no recent exercise) and in the blood drawing/processing procedure (ideally, blood drawn without a tourniquet, no hand clenching, blood drawn into a chilled tube and processed immediately) to minimize false elevations of lactates.

